1.0 Study Summary

Protocol Information	Description
Study Title	Growth, Empowerment, and Mindfulness (GEM): Pilot Trial of a Mindfulness-based Intervention to Address Mental Health in Young Adults with Early Life Adversities
Study Design	Single-arm feasibility study
Primary Objective	Examine the feasibility, acceptability, and preliminary efficacy of a mindfulness-based, app-delivered intervention to address mental health and emotion regulation challenges experienced by young adults with early life adversities (ELAs)
Secondary Objective(s)	Understand mechanisms of change underlying the intervention, including the role of mindfulness (i.e., interoceptive awareness and de-centering), rumination, and sleep using real-time data collection via ecological momentary assessments (EMAs) and wearable devices
Research Intervention(s)/ Investigational Agent(s)	Growth, Empowerment, and Mindfulness intervention
IND/IDE #	N/A
Study Population	Young adults aged 18-24 residing in the U.S.
Sample Size	$n = 44$ expected
Study Duration for individual participants	Total study duration for each participant is 3-4 months, comprising a baseline assessment, 4-6 weeks of active intervention, a post-intervention assessment, and a 3-month follow-up assessment.
Study Specific Abbreviations/ Definitions	EMA = Ecological Momentary Assessment EMI = Ecological Momentary Intervention ELA = early life adversity

2.0 Objectives

- 2.1 The objectives of this study are to: (a) examine the feasibility, acceptability, and preliminary efficacy of a mindfulness-based, app-delivered intervention to address mental health and emotion regulation challenges experienced by young adults with early life adversities (ELAs); and (b) understand mechanisms of change underlying the intervention, including the role of mindfulness (i.e., interoceptive awareness and de-centering), rumination, and sleep using real-time data collection via ecological momentary assessments (EMAs) and wearable devices.
- 2.2 We hypothesize that young adults will find the Growth, Empowerment, and Mindfulness (GEM) intervention to be both feasible and acceptable, as demonstrated by participants' engagement and quantitative/qualitative feedback; we also hypothesize that the engagement with the intervention will demonstrate preliminary efficacy for improving outcome measures including depression, anxiety, self-compassion, emotion regulation, loneliness, and healthier phone use. We further hypothesize that the mechanisms underlying the benefits of the intervention will be improvements in mindfulness and sleep, as well as reductions in rumination.

3.0 Background

- 3.1 mHEAL research team has extensive experience in developing and evaluating mindfulness-based, transdiagnostic interventions for young adults. Examples include Mindfulness-based Queer-Resilience (with over 200 pages of materials, 30+ created videos, and 50+ recorded audios in our lab library) for young adults with depression/anxiety and affected by trauma, stigma, and childhood adversity as well as Mindfulness for Pandemic Resilience, a mobile app for youth in China with psychiatric symptoms and affected by strict pandemic lockdowns. Both programs have been evaluated by RCTs and shown acceptability, feasibility, and preliminary efficacy. Findings showed that the intervention was efficacious especially for participants with experiences of early life adversities. However, there has not been a mindfulness intervention tailored specifically towards young adults who have lived experiences of early life adversities, representing an important opportunity for action. Further, studies that examine mechanisms underlying specific mindfulness practices and their effectiveness at addressing specific stressors are lacking.
- 3.2 N/A
- 3.3 Facing early life adversity is common among the United States population, with one epidemiological study finding that 53.4% of surveyed participants had experienced at least one adverse childhood event (Green et al., 2010). Early life adversity has been associated with poorer mental health, which can also contribute to a greater likelihood of engaging in risky health behaviors (Duffy et al., 2018). Additionally, early life adversity has been associated with alterations in neural functioning and compromised emotional regulation skills (Krugers et al., 2017). Mindfulness interventions have been found to reduce symptoms of anxiety and depression (Hofmann & Gómez, 2018) and improve emotional regulation abilities (Goldin &

4.0 Study Endpoints

- 4.1 We will collect quantitative and qualitative data from young adults, aged 18-24 (n=44). We will end data collection when the target sample size is reached or when sufficient data is collected to assess feasibility, acceptability, and preliminary efficacy outcomes (whichever comes first).
- 4.2 For safety endpoints, we will monitor for adverse events or any negative effects of the intervention; participants are free to withdraw from the study at any time, in which case their participation will end immediately with no penalty.

5.0 Study Intervention/Investigational Agent

- 5.1 The Growth, Empowerment, and Mindfulness (GEM) intervention is a structured, mindfulness-based intervention designed to offer support for young adults with early life adversities and their negative behavioral health consequences through

the development of awareness, emotion regulation, and adaptive coping skills. Through psychoeducation content, group practice sessions, and formal and informal mindfulness practices, GEM is aimed at helping participants build foundational mindfulness and self-compassion skills, increase interoceptive awareness, reduce experiential avoidance and de-centering, improve emotion regulation and decrease rumination, and integrate mindfulness skills into daily life. The specific content of the GEM intervention is currently under development with community feedback from relevant Community Advisory Board members (refer to “Intervention_GEM.docx” for drafted scripts of Weeks 1-4 and the Bonus Modules, which will guide the recorded materials; also refer to “Outline_GEM.docx” for intervention outline for each week).

- 5.2 Contents of the GEM intervention is delivered through an existing third-party mobile application (i.e., Expiwell) and consists of 4 weeks of “Recommended Modules” and 2 weeks of “Bonus Modules”. Each week, participants will gain access to a set of 5-11 modules, with each module combining formats of text and audio recordings of psychoeducational content and mindfulness practices. Each week’s modules are further divided into ‘core’ and ‘optional tailored’ modules.

	Recommended Modules (i.e., Weeks 1-4)	Bonus Modules (i.e., Weeks 5-6)
Core modules	Core modules in weeks 1-4 cover topics of early life stress and resilience, environmental stress and disembodied living, experiential avoidance, emotion regulation, mindful self-care, and self-compassion	Core modules in weeks 5-6 cover topics related to media consumption and purpose
Optional tailored modules	Throughout Weeks 1-6, Optional tailored modules will focus on topics of (a) minority stress for participants who identify as a minority member and (b) trauma for participants wanting to receive more information about trauma	

On the application, participants will also have access to a list of all mindfulness exercises that have been taught each week.

In addition to the weekly modules, participants will complete EMAs and EMIs 3 times per day during the Recommended Modules (i.e., first four weeks of intervention period). The EMI will be delivered concurrently with the EMA, which will collect participant’s response on their current mood, recent stressful experience, and type of stressor. Participants will then receive a list of mindfulness exercises, which will be tailored to the type of stressor/emotion they will have indicated. The intervention as well as EMAs and EMIs will be delivered on a mobile application named “Expiwell” (<https://www.expiwell.com/>).

At the end of each week, participants will also take part in a weekly “Group practice and connect” session on Zoom during the Recommended Modules (i.e., first four weeks of intervention period). The weekly sessions will be conducted in cohorts of 5-10 participants (depending on the recruitment speed), led by a research assistant who has previous experiences with mindfulness programs as well as lived experiences of early life adversity. Each session will last approximately one hour and will be structured roughly to reflect: group check-in, group discussion on past

week's weekly intervention content, one group meditation practice using audio, and reflections on the meditation practice.

- 5.3 This study will utilize Fitbit, a commercially available wearable device, for the purpose of passive data collection on sleep and physical activity. The Fitbit devices will be stored securely by the research team when not in use, distributed directly to participants during enrollment by mail, and collected at the end of the study. Names and addresses of participants will be shared with departmental operations staff through password-protected files to create shipping labels and facilitate mailing the Fitbits to participants via FedEx. When operations staff submit reconciliation for the transaction, it is on an aggregate level (i.e., without specific participant information or individual package tracking numbers). This ensures the confidentiality of each participant. Participants will be instructed on proper use and care of the device, and a pre-paid, pre-addressed return envelope will be provided so participants can directly mail the device back to the research team at the end of the study. Only authorized study team members will manage device distribution, collection, and data linkage.

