Data analysis: Feasibility, acceptability, and preliminary effects will be assessed using data from the T1, T2, and T3 surveys as well as EMA responses. Qualitative data analysis will also be performed for the exit-interviews and voice recordings to further qualify our findings after transcription and deidentification. Exit interviews will be transcribed using Dedoose (already vetted through OIT), while EMA voice recordings will be transcribed automatically through Expiwell's AWS service. Additionally, recruitment and retention rates, completion of weekly modules, adherence to daily EMA and EMI prompts, weekly session attendance, and other engagement metrics from the application (e.g., frequency of EMI-triggered vs. self-initiated practice use, time spent in modules) will be used to inform study and intervention feasibility.

- 6.3 We will take all reasonable precautions to prevent adverse events to participants. As a meditation-based intervention, a number of actions have been taken to minimize meditation-related risks at different stages of the study. During the pre-enrollment stage, individuals with severe mental

illness that could preclude regular class attendance or impact group participation (i.e., symptomatic, untreated bipolar disorder or a history of psychosis and/or schizophrenia) are excluded from the study. During treatment, meditations are created to be relatively short and interspersed with dyads and reflections to minimize probability of risk. Developing strategies for working with physical and emotional discomfort is also an explicit goal of the program.

No drugs will be administered as part of this study. The only devices used are a) the participant's personal cell phone with the intervention content loaded through the Expiwell app and b) a wearable device Fitbit, which is commercially available and FDA-cleared for general wellness monitoring; it will be used solely to collect sleep and physiological data.

For all assessments and guides used for data collection, please refer to the document named "Compiled measures_GEM.docx".

6.4 A list of all data that and how they will be collected during the study is listed below:

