Self-report data on feasibility, acceptability, and preliminary efficacy: Data on feasibility and acceptability as well as preliminary efficacy of the intervention on study outcomes (including mental health, functional impairment, emotion regulation, loneliness, mindfulness, self-compassion, stress, sleep, phone use, overall well-being, etc. – refer to Section 6.2 for full list of scales measured at each time point) will be collected via Qualtrics at baseline, post-intervention, 3-month follow-up, and weekly assessments during the first 4 weeks of intervention period (i.e., Recommended Modules).

EMAs: Daily self-reports on stress, mood, and emotional states will be collected on the Expiwell application. Furthermore, voice recordings for a "daily journal" will be collected during the last EMA of the day. Participants will be reminded that the voice recording is optional--they may skip voice recording submission without penalty and still receive compensation.

App engagement metrics: Frequency and duration of EMI-triggered and self-initiated mindfulness practice sessions will be collected on Expiwell.

Sleep metrics: Continuous objective data on sleep metrics (e.g., sleep latency, REM/non-REM sleep, sleep fragmentation, total sleep time, sleep efficiency) will be collected using wearable devices (i.e., Fitbits).

Semi-structured interviews: Qualitative feedback on intervention experience, feasibility, acceptability, and suggestions for improvement will be collected through a semi-structured Zoom interview with an RA.

6.5 Participants will complete a 3-month post-baseline follow-up survey after the 4-6-week intervention (4 weeks recommended, 2 weeks optional/bonus). Similarly to post-intervention survey, this assessment will collect self-report data on mental health, functional impairment, emotion regulation, loneliness, mindfulness, self-compassion, stress, sleep, phone use, overall well-being, etc. (refer to Section 6.2 for full list of scales measured 3-month follow-up).

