Pre-Post Changes (Clinical Outcomes) As a single-arm trial, we will use repeated measures ANOVA to assess preliminary changes in the primary clinical targets of depression (e.g., measured via PHQ-9) and anxiety (e.g., measured via GAD-7) from T1 to T2 (and T3 follow-up), characterizing within-group effect sizes using Cohen's *d*. To model individual clinical trajectories, we will use mixed-effects modeling with time entered as a fixed effect and participant as a random effect, incorporating relevant baseline covariates (e.g., age, gender, ELA severity).

EMA/Longitudinal Data Analysis

We will leverage the high-density EMA data using linear mixed-effects models to assess within-person, day-to-day, and moment-to-moment associations. Specifically, we will use time-lagged

analyses to evaluate the immediate, temporal impact of intervention engagement. For example, we will model whether the completion of an audio module at time t predicts significant reductions in momentary negative affect, anxiety, or perceived stress at the subsequent EMA prompt (time $t+1$). Additionally, we will visualize the interrelations between momentary stress, engagement with audio modules, and subsequent mood fluctuations via temporal network models.

To assess **momentary mechanisms**, we will utilize 1-1-1 Multilevel Structural Equation Modeling (MSEM). We will test whether momentary activation of specific psychological states (e.g., interoception, cognitive defusion, or acceptance/willingness) measured immediately post-EMI significantly mediates the relationship between EMI engagement at time t and reductions in negative affect at the subsequent EMA prompt (time $t+1$). We will conduct mediation analysis to understand which mechanism carries the largest indirect effect on symptom reduction. Additionally, we will visualize the interrelations between daily stressors, momentary mechanism activation, and subsequent mood fluctuations via temporal network models.

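### Each lagged EMA model names one GEM component as its exposure, so if components cluster in the same prompt interval, one can be credited with another's effect

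*Protocol*

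**What the plan says.** Protocol section 5.2 describes several components that run together in the first four weeks:

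- 5-11 modules a week, which themselves contain mindfulness practices.
- EMI exercises three times a day ("The EMI will be delivered concurrently with the EMA").
- An in-app list of the exercises taught so far, for self-initiated use.
- A weekly one-hour Zoom session with "one group meditation practice using audio, and reflections on the meditation practice".

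The first three are delivered in one app.

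The EMA/Longitudinal Data Analysis section of the SAP sets out to "evaluate the immediate, temporal impact of intervention engagement". Its worked example is "we will model whether the completion of an audio module at time t predicts significant reductions in momentary negative affect" at the next prompt. The 1-1-1 MSEM then asks whether momentary states carry a path that "mediates the relationship between EMI engagement at time t and reductions in negative affect at the subsequent EMA prompt". No covariates are listed for either model. The baseline covariates named in the SAP (age, gender, ELA severity) belong to the T1-T3 trajectory model. Group sessions and self-initiated practice appear in no lagged model.

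The other exposures are at least partly recorded. Protocol section 6.4 states: "Frequency and duration of EMI-triggered and self-initiated mindfulness practice sessions will be collected on Expiwell". Section 6.2 lists "weekly session attendance, and other engagement metrics from the application" among the feasibility data.

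**The concern.** Between two prompts a participant may finish a module, do an EMI exercise, start a practice and attend the group session. A model with one of these as its only exposure compares intervals that may also differ on the others. Within-person centring does not remove this, because the confounding would be within person and within interval. Person-level baseline covariates would not remove it either.

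Understanding mechanisms is the secondary objective (Protocol section 1.0), and the background names the lack of evidence on specific mindfulness practices as a gap. Attribution to a particular component is therefore what these models are for. An inert module could appear to lower negative affect, or an EMI effect could be overstated, and that reading could inform a later trial.

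**Working it through.** The plan gives no effect size, power or co-use figure for the EMA models, so there is nothing of its own to reproduce.

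**Inputs from the documents.** 3 prompts x 28 days = 84 prompts per participant. 4 group sessions. 5-11 modules a week x 4 = 20-44 modules. 44 participants, so 44 x 84 = 3,696 person-prompts at full adherence.

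**Assumed inputs.** Residual SD 1; 28 module completions per participant (share 28/84 = 1/3); practice in 40% of intervals; effect of the omitted component -0.3 SD; two-sided alpha 0.05; no missing prompts.

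**Formula.** For a binary exposure, bias in the module effect = effect of the other component x D, where D = P(other | module interval) - P(other | no module interval).

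**EMI-triggered or self-initiated practice, true module effect zero.** The standard error is about sqrt[1 / (3,696 x 1/3 x 2/3)] = sqrt(1/821) = 0.035. A simulation (300 replicates, person-centred regression in place of the mixed model) gave:

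| D | Formula bias (SD) | Simulated bias (SD) | Simulated false-positive rate |
|---|---|---|---|
| 0 | 0 | -0.001 | 5% |
| 0.10 | -0.3 x 0.10 = -0.03 | -0.029 | 13% |
| 0.30 | -0.3 x 0.30 = -0.09 | -0.088 | 69% |
| 0.50 | -0.3 x 0.50 = -0.15 | -0.149 | 99% |

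**Group session.** It touches 4/84 = 4.8% of intervals, or 12/84 = 14% if its effect lasts a full day. With immediate carry-over only, D is largest with 20 modules and every session in a module interval: 4/20 = 0.20. It is lowest with 44 modules and no session in a module interval: -4/(84 - 44) = -0.10. In the simulation, a session effect of -0.3 SD gave no bias when sessions were unrelated to module timing (-0.001 SD; false positives 4%). It gave -0.041 SD (24%) in the extreme case in which everyone attends and every session interval also contains a module completion.

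**Joint entry.** With module, practice and session in one equation, the module estimate was -0.001 to 0.003 SD and the false-positive rate 4-6% in every scenario. Here every component was measured and none was a consequence of another.

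**Direction for EMI.** The estimated EMI effect = true effect + other effect x D, with D now the difference between EMI and non-EMI intervals. With both effects at -0.20 SD, D = +0.25 gives -0.20 - 0.05 = -0.25, and D = -0.20 gives -0.20 + 0.04 = -0.16. Positive clustering inflates the EMI effect; dilution needs components to replace one another.

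**Practice as a mediator.** Suppose a module raises the chance of later practice by 20 points and practice lowers affect by 0.3 SD. The module's total effect is then 0.20 x -0.3 = -0.06 SD, all through practice. Adjusting for that later practice takes the module coefficient to about zero, although the module did help.

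**The case against.** The strongest reply is that sharing the same four weeks creates no bias in a within-person, interval-level model. Components must cluster in the same interval, and the omitted one must affect the next mood report. The documents give no co-use data, no prompt times and no session times relative to prompts. The module model is introduced as an example and the EMA covariates are left open, so joint modelling is not excluded. Protocol section 6.1 calls the outcome analyses exploratory, and no rule in the documents keeps or drops a component on a lagged coefficient. All of this stands. It limits the point to what can happen, and it is also why the covariates are best stated before the data are seen.

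A second reply concerns the remedy. Modules teach practices that then appear in the app list, so practice after a module may be its consequence. Adjusting for everything could remove a real module effect. This also stands and shapes the fix.

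Three stronger readings are tempting but unsupported:

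- A reader might infer that misattribution is certain. With D = 0 it is absent.
- A reader might take the group session as the main culprit because it has its own meditation and may prompt catching up on modules. The catch-up is conjecture, and the session touches few intervals.
- A reader might expect a real EMI effect to be diluted. If engaged moments bring several components together, the bias runs the other way.

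**Conclusion.** The point holds in conditional form. The SAP names one exposure per lagged model, the components run concurrently, and no mutual adjustment is stated. If components cluster within prompt intervals, which is plausible because three of them share one app, one can be credited with another's effect. EMI-triggered and self-initiated practice are the main potential source: about -0.03 to -0.15 SD of spurious module effect for clustering of 10 to 50 percentage points and a practice effect of -0.3 SD. The session is a minor source as long as its effect reaches only the next prompt. The clustering values, effect sizes and full adherence are assumptions.

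The consequence is confined to exploratory mechanism analyses. The feasibility and acceptability benchmarks and the T1-T3 changes for the whole package are unaffected. This is an inexpensive improvement and does not threaten the pilot's main conclusions.

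**What to change.** In the SAP's EMA section, for both the lagged models and the 1-1-1 MSEM:

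1. Add an indicator that a group session the participant attended fell between t and t+1.
2. Enter the other logged components that precede or coincide with the exposure (module completion, EMI-triggered practice, self-initiated practice), together with affect at t.
3. Report the model without later practice (total association) beside the model with it (direct association).
4. As a sensitivity analysis, drop the session intervals, at most 4 per participant.
5. Describe the results as associations, not as the impact of engagement.

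The cost is a few extra terms, slightly wider confidence intervals, and linking attended session times and practice logs to prompt intervals. Session days and times are set by cohort (Protocol section 6.2). For practice, section 6.4 promises frequency and duration, and section 7.1 names timestamps for EMA completions and other adherence information. The team should therefore confirm before enrolment that the Expiwell module and practice logs carry timestamps.
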